5. To evaluate the duration of mechanical ventilation in the postoperative period when using cryoablation of intercostal nerves and the standard treatment protocol in patients with minimally invasive mitral valve surgery.
6. Assess the length of stay in the ICU and the duration of hospitalization when using cryoablation of intercostal nerves and the standard treatment protocol.
7. Assess the presence of chronic post-thoracotomy pain syndrome in the postoperative period after 2 and 6 months and the presence of side effects after cryoablation of intercostal nerves (paresthesia in the area of surgical access and in the right arm).

Research participants

30 patients (15 patients in each group) who are scheduled to undergo minimally invasive mitral valve surgery under cardiopulmonary bypass.

Inclusion criteria

- Written informed consent;

- Minimally invasive mitral valve surgery.

Non-inclusion criteria:

- patient refusal;
- pregnancy;
- treatment with antidepressants or epileptic drugs;
- depression, which can significantly affect the perception of pain;
- chronic use of analgesics;
- participation in competing randomized clinical trials.

Exclusion criteria:

- Extended mechanical ventilation, more than 12 hours.

Randomization, allocation, blinding

A block will be used to distribute participants into groups randomization with block lengths of 2 and 4. Masking will be performed for the statistician. Sample size calculation was not performed because no data were available to estimate sample size.

Description and rationale for the route of administration, dosage, dosage regimen and course of treatment

Patients undergoing minimally invasive mitral valve surgery while on cardiopulmonary bypass will be randomized into two groups:

1. Patients receiving cryoablation of intercostal nerves (CryoINB) as a method of pain relief.
2. Patients who will undergo a standard pain management protocol.

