Patients in the CryoINB group will undergo cryoablation of the intercostal nerves, at the end of surgery before weaning from CPB, using the «ArtiCue» device for 120 seconds at a temperature of -50°C to -70°C, in the intercostal spaces where the surgical approach is located, one intercostal space above and one below it. Cold leads to axonotmesis, in which the axon and myelin sheath are damaged, preventing the pain signal from traveling along the sensory nerve. However, the structural elements of the nerve are preserved, which promotes complete regeneration at a rate of 1–2 mm per day, thereby restoring normal function within several months.

Patients in the group with the standard anesthesia protocol will receive an intercostal block in the area of surgical access - a single injection of 0.75% ropivacaine solution 20 ml. A local anesthetic will be injected into the area of the posterior wall of the chest 2 cm lateral to the sympathetic trunk under the parietal pleura in the intercostal space along the intercostal nerve, where the surgical approach is located [14].

All study participants will receive postoperative pain management according to the protocol described below:

If VAS >4 points on the scale, patients will receive NSAIDs (paracetamol 1 g IV) [15, 16]. The maximum daily dose will be 4 g/day.

If there is no effect after 30 minutes, opioid analgesics will be administered (MORPHINE 10 mg). The maximum daily dose of opioids for adults will be 50 mg.

If other opioid analgesics are administered, they will be converted to morphine equivalent (MME) [13].

Drug	Conversion factor to morphine	Conversion factor from morphine	Equianalgesic dose	
			IM/IV (mg)	PO (mg)
Morphine	1	1	10	30
Hydromorphone	×5	1/5	1.5	7.5
Oxycodone	×1.5	1/1.5	—	20
Hydrocodone	×1	×1	—	30
Fentanyl	×100	1/100	—	0.1
Codeine	/10	×10	130	200
Nalbuphine	×1	×1	—	—
Oxymorphone	×3	1/3	1	10
Tapentadol	×1	×1	—	—
Tramadol	/10	×10	100	120
Buprenorphine	×10	1/10	0.3	0.4 (SL)
Meperidine	/10	×10	100	300
Methadone	— ^a	— ^a	1	2

(Dott D., Sobey CM Common Opioids //Hospitalized Chronic Pain Patient: A Multidisciplinary Treatment Guide. – 2022. – P. 151.)

Primary outcome:

The opioid analgesic consumption within 48 hours after surgery, calculated in milligram morphine equivalent (MME).

Secondary endpoints:

- The intensity of pain, assessed using a visual analogue scale (VAS) after extubation, 6, 12, 24, 36, 48 hours after surgery

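### The opioid conversion table behind the primary outcome contradicts itself: in 7 of 13 testable cells the drug's factor does not return the table's own morphine reference

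*Protocol*

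**What the plan says.** The Primary outcome section defines the endpoint as "The opioid analgesic consumption within 48 hours after surgery, calculated in milligram morphine equivalent (MME").

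The section on the description and rationale of treatment names one postoperative opioid: "opioid analgesics will be administered (MORPHINE 10 mg"). It gives no route for it. For anything else it states: "If other opioid analgesics are administered, they will be converted to morphine equivalent (MME"). The table that follows has two parts:

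- a column headed "Conversion factor to morphine", with one value per drug and no route (a companion column gives the inverse factor);
- columns under "Equianalgesic dose", split into IM/IV and oral doses.

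The reference row is "Morphine 1 1 10 30": factor 1, 10 mg IM/IV, 30 mg oral. A typical drug row is "Hydromorphone ×5 1/5 1.5 7.5". The protocol does not say which part of the table governs, or whether MME means milligrams of parenteral or of oral morphine.

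**The concern.** Equianalgesic doses and conversion factors are two expressions of the same relation. If a dose of drug X is listed as equivalent to 10 mg of parenteral morphine, the factor for X by that route should turn that dose into 10. Where it does not, the table gives two different morphine equivalents for one administered dose.

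This table is the protocol's stated rule for building the primary endpoint. A patient given buprenorphine 0.3 mg IM/IV would add 3 MME by the factor and 10 MME by the dose column. The trial is also meant to supply planning data for a larger trial (Objectives), so an undefined MME scale could carry forward into that design.

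**Working it through.** **Inputs.** Factors and doses come from the conversion table; the references are the morphine row (10 mg IM/IV, 30 mg oral). The arm size of 15 comes from Research participants: "30 patients (15 patients in each group").

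**Check.** For each cell, printed factor × printed equianalgesic dose, compared with the morphine dose for the same route. Fold is the larger value divided by the smaller.

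| Drug | Route | Factor × dose | Result | Reference | Gap | Fold |
|---|---|---|---|---|---|---|
| Hydromorphone | IM/IV | 5 × 1.5 | 7.5 | 10 | −25% | 1.33 |
| Codeine | IM/IV | 130 / 10 | 13 | 10 | +30% | 1.30 |
| Oxymorphone | IM/IV | 3 × 1 | 3 | 10 | −70% | 3.33 |
| Buprenorphine | IM/IV | 10 × 0.3 | 3 | 10 | −70% | 3.33 |
| Tramadol | IM/IV | 100 / 10 | 10 | 10 | 0 | 1 |
| Meperidine | IM/IV | 100 / 10 | 10 | 10 | 0 | 1 |
| Hydromorphone | oral | 5 × 7.5 | 37.5 | 30 | +25% | 1.25 |
| Codeine | oral | 200 / 10 | 20 | 30 | −33% | 1.50 |
| Tramadol | oral | 120 / 10 | 12 | 30 | −60% | 2.50 |
| Oxycodone | oral | 1.5 × 20 | 30 | 30 | 0 | 1 |
| Hydrocodone | oral | 1 × 30 | 30 | 30 | 0 | 1 |
| Oxymorphone | oral | 3 × 10 | 30 | 30 | 0 | 1 |
| Meperidine | oral | 300 / 10 | 30 | 30 | 0 | 1 |

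Four of 6 IM/IV cells and 3 of 7 oral cells miss: 7 of 13. Taking 1.5-fold or more as material gives four. A 2-fold cut gives three, and a 25% cut gives all seven. The three smaller gaps (hydromorphone by both routes, IM/IV codeine) could be rounding.

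**Left out.**
- Fentanyl: 0.1 stands under oral, where 100 × 0.1 = 10 misses 30, but a column shift in the extracted text is possible. Counted as printed, the total is 8 of 14; counted as IM/IV, it matches and the total is 7 of 14.
- Sublingual buprenorphine: no sublingual morphine reference.
- Nalbuphine and tapentadol: no doses.
- Methadone: no factor.

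**Does one choice of scale repair it?** The six matching cells sit at two values: two at 10 and four at 30.
- Factors read as valid for oral doses only: 3 of 7 still miss, two of them materially.
- Factors read as valid for IM/IV doses only: 4 of 6 still miss, two of them materially.
- All 13 cells against 30: 6 IM/IV + 3 oral = 9 miss.
- All 13 cells against 10: 4 IM/IV + 7 oral = 11 miss.

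Morphine shows the route problem too: with factor 1, the two doses listed as equivalent score 10 and 30 MME, a 3-fold gap.

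**Size in the endpoint.** Shift in a 15-patient arm mean for one table-sized dose, factor value minus equianalgesic value:

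| Dose | MME on 10 mg parenteral scale | MME on 30 mg oral scale |
|---|---|---|
| Oxymorphone 1 mg or buprenorphine 0.3 mg, IM/IV | (3 − 10)/15 = −0.47 mg | (3 − 30)/15 = −1.80 mg |
| Tramadol 120 mg, oral | (12 − 10)/15 = +0.13 mg | (12 − 30)/15 = −1.20 mg |
| Codeine 200 mg, oral | (20 − 10)/15 = +0.67 mg | (20 − 30)/15 = −0.67 mg |

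The number of such doses is not stated. With morphine by one route the shift is 0.

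**The case against.** The strongest reply is that the column labelled as the conversion factor is plainly the one to use, and that the equianalgesic doses are background. Each dose would then enter the endpoint once, by the same rule in both arms. This is a fair reading, and it weakens the claim that staff would face two answers. It does not remove the error: the rule would still credit some doses with less than a third of what the adjacent column calls equivalent, and it would still ignore route.

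The reply on impact is also strong. Morphine is the only postoperative opioid named, its 10 mg dose equals the table's IM/IV reference, and paracetamol is specified as intravenous. If all rescue is parenteral (an assumption), the oral gaps never arise, and tramadol and meperidine convert consistently. The IM/IV gaps for oxymorphone and buprenorphine would remain, but nothing in the protocol says these drugs are expected. This stands, and it limits the seriousness of the point.

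Two smaller objections also stand. The 1.5-fold line is a judgement. The common-scale counts of 9 and 11 partly restate the table's 3:1 oral-to-parenteral morphine ratio, so the same-route count of 7 is the one to rely on.

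The table is attributed to a cited source that is not available here, so it cannot be said whether the conflict arose in the source or in transcription. The rows counted do print complete entries, and their forward and inverse factors are exact reciprocals, so garbled extraction is an unlikely explanation.

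**Conclusion.** The concern holds. The table that defines MME for the primary outcome is internally inconsistent in 7 of 13 same-route cells, four of them by 1.5-fold to 3.3-fold, and no single reference route reconciles it. The arithmetic is certain for the rows as printed. The consequence is conditional: it needs a non-morphine opioid, or more than one route, within the 48 hours. The protocol provides for other opioids but gives no expected frequency, so the total effect cannot be sized beyond the per-dose shifts, and no direction of bias between arms can be inferred. It should be corrected because it sits in the primary endpoint's definition, but it does not by itself put the trial's result in doubt.

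**What to change.** For the endpoint calculation only:

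1. Check the factor column and the dose columns against the cited source and reconcile them, without presuming which is right.
2. State whether MME means parenteral or oral morphine.
3. Convert every dose, including morphine given by another route, with one set of route-specific factors on that scale.
4. Make sure the drug, dose and route of each postoperative opioid administration are available. The list of data for the hospital and ICU period names only a 48-hour dose already expressed in MME, from which a conversion could not be redone.

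The cost is a corrected table and, if it is not already charted, a route entry for each opioid dose. Treatment does not change.

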- Dynamics of spirography (FEV1, FVC) before surgery, 48 hours after surgery, before the patient's discharge
- Frequency of side effects (nausea, vomiting, etc.)
- Need for inotropic/vasopressor support
- Duration of mechanical ventilation
- Duration of ICU stay
- Duration of hospital stay
- Follow-up after 2 and 6 months (CPPS, numbness in the right arm and in the area of surgical access)

Statistical analysis

Comparisons of continuous outcomes will be made using the Mann-Whitney test for non-normal variables and the Welsh t test for normal variables. Comparisons of binary outcomes will be made by the chi-square test or Fisher's exact test.

Data processing

All information will be collected by staff using paper documentation, the data of which will then be entered into an electronic database.

Initial data

1. Demographic indicators: age, gender, height, weight, body mass index.
2. Disease severity: left ventricular ejection fraction, left ventricular EDV, presence of mitral regurgitation, degree of mitral regurgitation, peak mitral valve gradient, pulmonary artery pressure, FAC (Fractional Area Change), history of cardiac surgery, NYHA class, EuroSCORE II risk.
3. Concomitant diseases: myocardial infarction, arterial hypertension, diabetes mellitus, atrial fibrillation, ventricular extrasystole, COPD, chronic kidney disease, stroke, epilepsy.
4. Taking the following medications: antidepressants, antiepileptic drugs, long-term use of NSAIDs (more than 14 days), opioid analgesics.

During the operation:

1. Type of surgery (mitral valve repair or replacement).
2. Time of heart-lung bypass (minutes).
3. Aortic occlusion time (minutes).
4. Minimum temperature during surgery.
5. Dose of fentanyl per operation (mg/kg).
6. Inotropic index.

Period of hospitalization and stay in the ICU:

1. Dose of opioid analgesics 48 hours after surgery (morphine in MME).
2. Assessment of pain intensity using a visual analogue scale (VAS) after extubation, 6, 12, 24, 36, 48 hours after surgery.
3. Duration of mechanical ventilation (in days).
4. The presence of side effects (nausea, vomiting).
5. Need for inotropic and vasopressor support, VIS.
6. Surgery complications (pulmonary edema, bleeding, febrile seizures, heart failure, respiratory failure, myocardial infarction).
7. Duration of stay in the ICU (in days).
8. Duration of hospitalization (in days).
9. The result of spirometry before surgery, 48 hours after surgery and before

discharge.

Ethical issues

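### Ventilation duration, a secondary endpoint, is recorded in days with no stated precision, although retained patients can have at most half a day of it

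*Protocol*

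**What the plan says.** Four places in the protocol bear on this.

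- **Exclusion criteria.** The only entry is "Extended mechanical ventilation, more than 12 hours". It stands apart from the non-inclusion criteria and can be known only after surgery.
- **Research aims, item 5, and Secondary endpoints.** Ventilation time is to be compared between the arms: "To evaluate the duration of mechanical ventilation in the postoperative period when using cryoablation of intercostal nerves and the standard treatment protocol".
- **Period of hospitalization and stay in the ICU (data list).** The item reads "Duration of mechanical ventilation (in days)". No decimals or rounding rule are given. ICU stay and hospital stay in the same list are also in days. The list for the operation uses a finer unit, for example "Time of heart-lung bypass (minutes)", and aortic occlusion is also in minutes. No extubation date or time is listed, and the start point of ventilation duration is not defined.
- **Secondary endpoints, VAS.** The schedule is "The intensity of pain, assessed using a visual analogue scale (VAS) after extubation, 6, 12, 24, 36, 48 hours after surgery", and the data list repeats it.

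For the test, the Statistical analysis section says "Comparisons of continuous outcomes will be made using the Mann-Whitney test for non-normal variables", with a Welch t test for normal variables.

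**The concern.** The whole range that a retained patient can take on this endpoint is half of one recording unit. If staff enter whole days, every retained patient has the same value, and neither planned test can show a difference whatever the treatment does. If they enter half days, much of the information goes. An SAP cannot restore times that were never recorded. The trial is a pilot meant to supply data for planning a larger one, and a usable distribution of ventilation times is part of that.

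A secondary matter follows from the same limit. A patient extubated between 6 and 12 hours after surgery is retained but cannot give a self-reported VAS at 6 hours. The 6-hour comparison then rests on patients already extubated. Readers would want the number not yet extubated in each arm, and a recorded extubation time gives it directly.

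**Working it through.** The protocol derives no power or sample size figure, so there is nothing of its own to reproduce.

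**Inputs from the protocol:** 12-hour limit; recording in days; 15 patients per arm; Mann-Whitney test; VAS at 6 hours. **Assumed, because the protocol gives none:** log-normal ventilation times, their medians and log-SD, two-sided alpha 0.05, and the correlation of ventilation time with pain.

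**Step 1, units.** 12/24 = 0.5 day and 6/24 = 0.25 day. For durations up to 12 hours:

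- whole days: one value (0 if rounded down, 1 if rounded up);
- one decimal: 6 values, 0.0 to 0.5;
- two decimals: 51 values, each about 0.24 hour wide.

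**Step 2, power.** Simulation with 15 per arm from log-normals truncated at 12 hours, 4,000 replicates. Results at log-SD 0.5:

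| Medians | Hours | Tenths of a day | Nearest half day | Whole days |
|---|---|---|---|---|
| 5 v 3 h | 71% | 65% | 39–40% | 0 |
| 6 v 4 h | 46% | 43% | 29% | 0 |

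Two-decimal days match hours to within simulation error (71–72% at 5 v 3 h). With log-SD from 0.4 to 0.6, the 5 v 3 h row runs over about 51–90%, 46–84%, 28–51% and 0. With equal medians of 4 h, the rejection rate in hours is 4.6–5.0%, so the test holds its level. If half days are rounded up, every retained patient has 0.5 and nothing can be compared.

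**Step 3, retained patients still ventilated at 6 hours.** The share is P(6 < T ≤ L) / P(T ≤ L), where T runs from the end of surgery. L = 12 if the 12-hour count also starts there, and L = 12 − a if it starts a hours earlier. For log-SD 0.4 to 0.6:

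| Median | L = 12 | L = 8 (a = 4) | L = 6 (a = 6) |
|---|---|---|---|
| 3 h | 4.1–11.5% | 3.5–7.7% | 0 |
| 4 h | 15–22% | 12–14% | 0 |
| 6 h | 43–48% | 27–35% | 0 |

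The range is therefore 0 to 48%, or 0 to about 7.2 of 15 per arm (0.48 × 15).

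**Step 4, can days already identify these patients?** 6 hours is 0.25 day, which is a rounding boundary. In tenths, 0.2 or less means below 6 hours and 0.3 or more means above. In nearest half days, 0 and 0.5 split at the same point. Of 1,000,000 draws over 0–12 hours, none was misclassified in either format. This holds if ventilation is counted from the end of surgery. It fails in whole days or rounded-up half days.

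**Step 5, bias of the 6-hour VAS with no true effect.** With correlation r between log ventilation time and pain, the difference in mean VAS is r × (E[z | z < c₂] − E[z | z < c₁]), in SD units. Here c = ln(6/median)/0.5 and E[z | z < c] = −φ(c)/Φ(c).

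- 4 v 3 h: −0.166 − (−0.363) = 0.197. Multiplied by r = 0.2 and 0.4, this gives 0.04 and 0.08 SD.
- 6 v 4.5 h: −0.471 − (−0.798) = 0.327, giving 0.07 and 0.13 SD.
- Equal medians: 0.

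For comparison, the 95% CI half-width is t(0.975, 2n − 2) × √(2/n): 0.75 SD with 15 per arm and 1.07 SD with 8.

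**The case against.** The strongest reply is that whole days are nowhere stated. The analysis section treats durations as continuous outcomes, and a duration in days can carry decimals: two decimals lose nothing and one decimal little. Staff must also know ventilation to the hour to apply the 12-hour limit, so the source notes may hold it. This stands. A reader might infer that the protocol makes the endpoint impossible to compare, but that is true only under one unstated recording convention. What remains is that the unit fits the endpoint badly and no precision protects it.

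A reader might also infer that the number of patients unable to give a 6-hour VAS cannot be reported by arm. Step 4 shows otherwise for tenths and nearest half days when the count starts at the end of surgery. Nor does the absence of extubation time from a summary list prove that it goes unrecorded, since a VAS after extubation requires staff to note that event.

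A third tempting reading is that the 6-hour VAS is so selected that no between-arm conclusion should be drawn from it. The bias in step 5 is small beside the CI, and this is one of six readings of a secondary endpoint, so that would be disproportionate. How to code a reading that fell due before extubation is ordinary case-report-form or SAP detail.

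Finally, the 0.5-day ceiling assumes that the exclusion criterion removes patients after randomization. That is the natural reading, but the protocol does not say so outright.

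**Conclusion.** The point holds as a mismatch between the 12-hour exclusion limit and a recording unit of days for an endpoint the trial means to compare. Its size depends on how the days are entered: nothing lost at two decimals, little at one, roughly 30 percentage points of power at nearest half days in the 5 v 3 h illustration (71% to about 40%), and everything in whole days. These figures rest on assumed ventilation times and alpha, and on the exclusion acting after randomization.

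The 6-hour VAS matter is real but secondary: 0 to 48% of retained patients affected and 0 to 0.13 SD of bias, all under assumption. The primary outcome is not touched. Severity is minor.

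**What to change.** In the protocol's data list for hospitalization and ICU stay, change the unit for mechanical ventilation from days to hours. Derive it from a recorded extubation date and time, and state the start point of the duration (for example the end of surgery). With that field in place, report by arm, alongside the 6-hour VAS result, how many retained patients were still ventilated at that time.

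The cost is one changed unit and one time field. No assessment is added and no clinical rule changes. The change does not deal with any selection caused by the 12-hour exclusion itself.

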Protocol Clinical Trial

**Effect of cryoablation of intercostal nerves on
pain in the early postoperative period in
patients with minimally invasive mitral valve
surgery: a pilot prospective randomized
study (BLOCK trial).**

NCT number: NCT06443931

Date: 05.04.2024

Background

Cardiovascular diseases are one of the main causes of death worldwide. According to pathological studies, heart defects occur in 4-7% of cases, and the most common defect among the defects is damage to the mitral valve [1]. Significant advances in surgical practice, instrumentation, tissue manipulation, and perfusion technology have made it possible to perform mitral valve surgery using mini-approaches. Minimally invasive mitral valve surgery has become the standard of care in some specialized cardiac centers around the world due to its excellent results, even despite longer cardiopulmonary bypass times and aortic occlusion. In 2008, P. Modi and co-authors, a meta-analysis has been published in which the authors come to the conclusion that a minimally invasive approach for correcting mitral valve pathology actually has significant advantages: early activation of patients, shorter duration of stay in the recovery room, shorter wound healing times, advantages in case of repeated interventions, less the number of bleedings and purulent-septic complications compared to classical sternotomy [2]. But despite all the advantages of this approach, severe pain after minimally invasive cardiac surgery continues to remain a serious problem [3]. Acute pain occurs after dissection of the chest, pleura and pericardium, compression of the intercostal nerve with a retractor, as well as dissection of the intercostal and pectoral muscles during surgical access. It limits breathing and cough in the postoperative period, which can subsequently lead to hypoxemia, sputum stagnation, atelectasis, pneumonia, myocardial ischemia, slow recovery, and also an increase in the length of hospitalization [4]. Therefore, additional emphasis and attention is paid to protocols for early functional restoration and pain reduction for this group of patients. There are protocols for “enhanced recovery after surgery” (ERAS - Enhanced Recovery After Surgery), their use makes it possible to achieve shorter stays in the intensive care unit, reduce hospitalization, improve treatment outcomes and reduce financial costs. One of the components of ERAS is the use of additional pain management modalities [5]. However, in cardiac surgery, traditional methods of regional anesthesia, such as thoracic epidural anesthesia or paravertebral block, are not usually used due to intraoperative heparinization and the associated higher risk of spinal or epidural hematoma. Finding an optimal and effective pain management strategy for this category of patients remains an unsolved problem today.

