In 2021 Peter I Cha and others published a systematic review of 23 studies on the effectiveness of intercostal cryoneurolysis in patients with pectus excavatum, lateral thoracotomy, post-thoracotomy pain syndrome, traumatic rib fracture and chest wall malignancy. Most studies have demonstrated a reduction in opioid analgesic use with intercostal nerve cryoablation compared with traditional pain management techniques. In patients requiring lateral thoracotomy, intercostal cryoablation results in decreased opioid analgesic dosage (grade 2A) and improved pain scores (grade 2C) postoperatively (PICO guidelines) [11].

Finding an effective and at the same time simple strategy for pain relief in the early postoperative period in patients undergoing minimally invasive mitral valve surgery is an urgent task; it is advisable to conduct a prospective clinical study with a well-thought-out design in this direction.

Study design

A single-center pilot prospective randomized clinical trial is planned, with a 1:1 allocation ratio.

Objectives

To determine whether cryoablation of intercostal nerves provides a clinically significant analgesic effect, which is reflected in a decrease in opioid analgesics consumption and in a decrease in pain according to VAS in patients undergoing minimally invasive mitral valve surgery. To obtain preliminary data for planning a subsequent larger prospective randomized trial.

Research aims:

1. Conduct a comparative analysis of the data on the opioid analgesic consumption necessary for pain relief when using cryoablation of intercostal nerves and the standard treatment protocol in patients with minimally invasive mitral valve surgery.
2. To conduct a comparative assessment of pain syndrome according to VAS in patients in the intercostal nerve cryoablation groups and the standard treatment protocol in patients with minimally invasive mitral valve surgery.
3. Assess spirometry parameters (FEV1, FVC) before surgery, 48 hours after surgery and before discharge when using cryoablation of intercostal nerves and the standard treatment protocol in patients with minimally invasive mitral valve surgery.
4. To evaluate the incidence of side effects and the need for inotropic and vasopressor support in the early postoperative period in the intercostal nerve cryoablation and standard treatment protocol groups in patients undergoing minimally invasive mitral valve surgery.

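### The pre-discharge spirometry has no fixed day, so its between-arm comparison can mix lung function with recovery time; the 48-hour value adjusted for baseline is the sounder comparison

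*Protocol*

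**What the plan says.** The Protocol gives the same three spirometry time points in three places:

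- Secondary endpoints: "Dynamics of spirography (FEV1, FVC) before surgery, 48 hours after surgery, before the patient"'s discharge.
- Research aims, item 3: "Assess spirometry parameters (FEV1, FVC) before surgery, 48 hours after surgery and before discharge when using cryoablation of intercostal nerves", with the standard protocol as the other arm.
- Data list for the hospital and ICU period, item 9: "The result of spirometry before surgery, 48 hours after surgery and before" discharge.

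The 48-hour reading is fixed. The last reading is tied only to discharge: there is no postoperative day, no window and no statement of discharge criteria. The data list includes length of hospitalization in days but no date for the spirometry test.

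Length of stay is also an outcome. It is a secondary endpoint ("Duration of hospital stay") and research aim 6 ("Assess the length of stay in the ICU and the duration of hospitalization when using cryoablation of intercostal nerves and the standard treatment protocol"). The Background names, among the possible consequences of acute pain that restricts breathing and coughing, "slow recovery, and also an increase in the length of hospitalization".

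Under Statistical analysis, the only method for continuous endpoints is: "Comparisons of continuous outcomes will be made using the Mann-Whitney test for non-normal variables and the Welsh t test for normal variables". No covariate and no allowance for time since surgery is mentioned. Masking is stated for the statistician only.

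**The concern.** A reading taken at discharge is taken at a time that follows randomization and may depend on the arm. The Protocol itself describes the path: treatment acts on pain, and pain may act on length of stay. If one arm goes home sooner while lung function is still improving, its patients are measured at an earlier point on their recovery curve. Their FEV1 and FVC will look lower even if the two recovery curves are identical. If cryoablation shortened stay, the distortion would run against cryoablation. Nothing in the Protocol provides for masking the staff who decide discharge.

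This matters because the pilot is meant to supply data for planning a larger trial, and a spirometry difference that reflects timing could be carried forward as a treatment effect.

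A second, smaller point concerns precision. The preoperative FEV1 and FVC are collected, but neither stated test adjusts for them. With 15 patients per arm, that is information worth using.

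**Working it through.** The Protocol has no spirometry calculation to reproduce, and it states that no sample size calculation was done. The only input from the document is 15 patients per arm. All other inputs are assumptions, including the unit, because the Protocol does not say how FEV1 and FVC will be expressed.

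**Timing distortion**

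Assumptions: recovery g = 1 to 3 points of % predicted per day; difference in stay d = 0 to 2 days; SD = 10 to 15 points; discharge day unrelated to the patient's own lung function; no true effect on the recovery curve.

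- Difference at discharge = effect at a common time − g × d.
- SE of a difference in means = SD × √(2/15), which is 10 × 0.365 = 3.65 or 15 × 0.365 = 5.48 points.

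| Difference in stay | Distortion g × d (points) | In SE units | Rejection rate at 5%, no true effect |
|---|---|---|---|
| 0 days | 0 | 0 | 5% |
| 1 day | 1 to 3 | 1/5.48 = 0.18 to 3/3.65 = 0.82 | 5.4% to 13% |
| 2 days | 2 to 6 | 2/5.48 = 0.37 to 6/3.65 = 1.64 | 6.5% to 38% |

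The rejection rates use the normal approximation. A simulation of 20,000 runs also let discharge day vary between patients (assumed lognormal, median 8 days, log-scale SD 0.25). The rates were lower:

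- g = 2, d = 2, SD = 10: mean difference −4.0 points; rejection 16% (Welch) and 15% (Mann-Whitney), against 19.5% by the approximation.
- g = 2, d = 2, SD = 15: mean difference −4.0 points; rejection 10% and 9%.
- g = 2, d = 0, SD = 10: mean difference 0; rejection 4.8% and 4.5%, so both tests hold their level when stays do not differ.

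At a common time d = 0 by design, so the distortion is zero. The 48-hour reading already has this property.

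**Baseline adjustment**

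Assumptions: correlation r = 0.5 to 0.8 between the preoperative and 48-hour values, with equal variances at both times.

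- ANCOVA against raw 48-hour values: variance ratio 1 − r². At r = 0.5 it is 0.75 (a 25% cut, equivalent to 15/0.75 = 20 per arm). At r = 0.8 it is 0.36 (a 64% cut, equivalent to 15/0.36 = 41.7 per arm).
- ANCOVA against change from baseline: variance ratio (1 − r²)/[2(1 − r)] = (1 + r)/2. At r = 0.5 it is 0.75 (a 25% cut, 20 per arm). At r = 0.8 it is 0.90 (a 10% cut, 15/0.90 = 16.7 per arm).

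Which comparator applies depends on what the endpoint's word for change over time means, and the Protocol does not define it.

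**The case against.** The strongest reply is that no bias has been shown. Two conditions must both hold: stays must differ between arms, and FEV1/FVC must still be changing at discharge. The Protocol gives no figure for either. It also never says that the discharge value is meant to estimate an effect on a given day. As a comparison of patients' condition on leaving hospital, it is protected by randomization. All of this stands, so a reader who infers that the discharge comparison is biased outright goes further than the document allows.

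A reader might also infer that cryoablation is intended to shorten stay. The Protocol does not say so. Its objective concerns opioid consumption and pain, aim 6 only assesses stay, and the Background describes a possible consequence of pain.

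Nor is the mechanism settled. If patients go home once they reach a similar level of recovery, discharge values would converge and real differences would be hidden, rather than a spurious gap created. Without discharge criteria the document cannot tell the two apart, and the 0-6 points apply only to the case where discharge day is unrelated to lung function. With SEs of about 3.7 to 5.5 points, much of that range lies within one SE.

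On baseline, a reader might infer that the preoperative value goes unused. The endpoint can reasonably be read as change from baseline, and either stated test can be run on changes. What stands is narrower: it is not used as a covariate, and against change scores the gain shrinks to 25-10%.

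Finally, the choice of model and of leading time point often belongs in an SAP, which is not shown. That is fair for the ANCOVA part, although the Protocol does name a method and a better one is available. It does not cover the timing: if the day of the reading is neither fixed nor recorded, a later analysis plan cannot recover it. Adjusting for length of stay is not a clean repair either, because stay is itself a post-randomization outcome.

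**Conclusion.** The point holds in a conditional and limited form. The pre-discharge reading has no common time, and its timing depends on an outcome that the Protocol studies and links to pain. If stays differ while lung function is still recovering, the discharge comparison can be biased for the effect at a common time. The size is about 0-6 points of % predicted, assuming recovery of 1-3 points per day and stays 0-2 days apart. If stays are equal, the expected distortion is zero.

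The precision gain from ANCOVA at 48 hours is 25-64% of the variance against raw values, or 25-10% against change scores, for correlations of 0.5-0.8 and equal variances. None of these inputs comes from the Protocol.

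Only one of two postoperative time points of one secondary endpoint is affected by the timing problem. The primary endpoint is untouched. This is a desirable improvement, not a flaw that threatens the trial.

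**What to change.** - State that the between-arm spirometry comparison is FEV1 and FVC at 48 hours, each analysed by ANCOVA with the preoperative value as covariate.
- Add the postoperative day of the discharge spirometry to the data list.
- Report the discharge values descriptively by arm, together with the day on which they were taken.

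The cost is a change of wording and one recorded date. There is no new measurement and no change to treatment. The downside is small: the discharge value has no formal test, and the covariate uses one degree of freedom (with all 30 patients, residual degrees of freedom fall from 30 − 2 = 28 to 30 − 3 = 27).
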